##### 9.1.2. Sensor Failure Criteria

A Sensor failure occurs when no readings can be obtained from it after troubleshooting the system to rule out any problems with the external electronics.

*This confidential document is the property of Abbott and shall not be reproduced, distributed, disclosed or used without the express written consent of Abbott*

## Clinical Investigation Plan

### **10. EFFECTIVENESS ANALYSES**

#### **10.1. Primary Effectiveness Endpoint**

The primary effectiveness endpoint will compare the annualized HF hospitalization rate at 1 year in the study to the HF hospitalization rate in the year prior to enrollment.

#### **10.2. Supplemental Analyses**

##### **10.2.1. Mortality**

The mortality rate at 1 year in study will be analyzed.

##### **10.2.2. HF Hospitalization or Death**

The annualized HF hospitalization or death rate at 1 year in the study will be compared to the HF hospitalization rate in the year prior to enrollment.

##### **10.2.3. Patient Compliance**

Patient device usage over the course of the trial will be examined.

##### **10.2.4. Quality of Life Evaluation**

Quality of Life will be measured using the EuroQOL Five Dimensions Questionnaire (EQ-5D-5L).

##### **10.2.5. Subgroup Analyses**

The effectiveness analyses will be evaluated in each of the following subgroups: Women, Men, Reduced Ejection Fraction (< 40%), Preserved Ejection Fraction ( $\geq 40\%$ ), Ischemic Etiology, Non-ischemic Etiology, With ICD/CRT-D, and Without ICD/CRT-D.

##### **10.2.6. Subject Contact**

Frequency, purpose and outcome of all contacts between site staff and study subjects post implant will be examined.

## Clinical Investigation Plan

### **11. ADVERSE EVENTS**

#### **11.1. Adverse Event (AE)**

An adverse event (AE) is any untoward medical occurrence, unintended disease or injury, or untoward clinical signs (including abnormal laboratory findings) in subjects, users or other persons, whether or not related to the medical device under investigation.

Note 1: This definition includes events related to the medical device under investigation or the comparator.

Note 2: This definition includes events related to the procedures involved.

Note 3: For users or other persons, this definition is restricted to events related to medical devices under investigation.

#### **11.2. Serious Adverse Event (SAE)**

If the AE meets any of the criteria below, it is regarded as a serious adverse event (SAE).

- a) Led to a death,
- b) Led to a serious deterioration in health of the subject, that either resulted in
  - 1. a life-threatening illness or injury, or
  - 2. a permanent impairment of a body structure or a body function, or
  - 3. in-patient hospitalization or prolongation of existing hospitalization, or
  - 4. medical or surgical intervention to prevent life threatening illness or injury or permanent impairment to a body structure or a body function.
  - 5. chronic disease
- c) Led to fetal distress, fetal death or a congenital abnormality or birth defect.

**Note:** A planned hospitalization for pre-existing condition, or a procedure required by the CIP, without a serious deterioration in health, is not considered to be an SAE.

#### **11.3. Device-Relatedness**

An AE or SAE that is definitely or possibly related to the device or the insertion procedure should be considered device-related. A serious adverse device effect (SADE) is an event that meets any of the above SAE criteria and is considered definitely or possibly related to the device or the insertion procedure by the Investigator. All other events considered definitely or possibly related to the device or insertion procedure are non-serious adverse device effects (ADEs).

If it is not certain that an event meets the above definitions, contact the Study Manager.

#### **11.4. Device Deficiency**

Device deficiency is defined as inadequacy of a medical device with respect to its identity, quality, durability, reliability, safety or performance.

Device deficiencies will not be collected on the case report forms for this study.

### 11.5. Procedures for Reporting Adverse Events

Safety surveillance and reporting starts as soon as the patient is enrolled in the clinical investigation. Safety surveillance and reporting will continue until the last follow-up visit has been performed, the subject is deceased, the subject concludes participation in the clinical study or the subject withdraws from the clinical study. All ADEs, SAEs, and SADEs, including deaths, will be collected throughout the time period defined above and will be reported to the Sponsor on a CRF.

The investigator should report all SAEs to the Sponsor as soon as possible but no later than outlined below.

Clinical Site	Reporting timelines
All Sites	SAEs must be reported to the Sponsor no later than 3 calendar days from the day the site personnel became aware of the event or as per the investigative site's local requirements, if the requirement is more stringent than those outlined.

The date the site staff became aware the event met the criteria of an SAE must be recorded in the source document. The Investigator will further report the SAE to the local EC according to the institution's EC reporting requirements.

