## Clinical Investigation Plan

### **12. STATISTICAL ANALYSIS**

The data will be summarized using univariate statistics (e.g., N, mean, standard deviation, median, minimum and maximum) or frequency (e.g., N, %) as appropriate for continuous or categorical variables, respectively.

The primary time point for safety analyses is 24 months post enrollment. Enrollment is defined as having a successful Sensor implant. The primary time point for effectiveness analyses is 12 months post enrollment.

Unless otherwise specified, all statistical tests will be 2-sided with a significance level of 0.05.

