#### **12.1. Populations for Analysis**

**Safety Population:** The Safety Population consists of all subjects who received a Sensor implant or underwent the implant procedure but were never implanted, regardless of study completion status. All safety analyses will be performed on the Safety population.

Subjects who are found not to have an appropriately sized pulmonary artery branch and did not receive the Sensor implant will be considered ineligible for the study. However, these subjects will be followed for 30 days for safety and all safety related data for these subjects will be provided.

**Effectiveness Population:** The effectiveness population consists of all subjects who received a Sensor implant regardless of study completion status. All effectiveness analyses will be performed on the effectiveness population.

**Pooled Safety Population:** The Pooled Safety Population will consist of the Safety Population from this study and the Safety Population from other similar study(ies) (demonstrated to be poolable with this study) that have been combined to form a larger safety analysis population to permit more robust analyses.

**Pooled Effectiveness Population:** The Pooled Effectiveness Population will consist of the Effectiveness Population from this study and the Effectiveness Population from other similar study(ies) (demonstrated to be poolable with this study) that have been combined to form a larger effectiveness analysis population to permit more robust analyses.

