## Clinical Investigation Plan

### **21. APPENDIX F: Protocol Definitions**

**Enrollment** – After signing the Informed consent, meeting study inclusion criteria and following successful Sensor implant, subjects are considered enrolled.

**HF Hospitalization** – A HF hospitalization of greater than or equal to 24 hours in a hospital

**Active Infection**- Febrile, elevated WBC, left shift, on antibiotics, positive cultures (blood, sputum or urine).

**PI** – Appropriate clinician designated as the Principal Investigator on the “Investigator Agreement” received and approved by St. Jude Medical. For study related procedures/visits PI refers to the PI or his/her designee.

**Source documents** – Primary study documentation including electronic, paper, phone messages, etc. containing study-pertinent information such as visit information, clinical history, medications, (S)AE reporting, etc. These documents are originals and should be treated as such. Information from these documents will be transferred from and compared against information reported in study CRFs.

**Sub-investigator** – Clinical personnel designated as a sub-investigator on the “Investigator Agreement” received and approved by St. Jude Medical.

**Worksheets** –Source documents used for calculation of clinical values such as BMI or EGFR from screening to end of study. Worksheets may also be used during the sensor implant or follow-up visits to capture information not captured in the medical record. In order for these worksheets to be considered valid, the Investigator must sign and date the worksheet.

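### Adverse event collection is tied to successful implant, in conflict with the Safety Population, and sensor failure is analysed on a population that includes subjects with no sensor

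*Combined protocol and SAP*

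**What the plan says.** **Collection window.** Section 11.5 opens surveillance at enrollment ("Safety surveillance and reporting starts as soon as the patient is enrolled in the clinical investigation") and says that ADEs, SAEs and SADEs "will be collected throughout the time period defined above". Section 12 states: "Enrollment is defined as having a successful Sensor implant". Appendix F agrees: "following successful Sensor implant, subjects are considered enrolled". The synopsis instead enrolls on consent plus eligibility and does not name the implant.

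**Population.** Under section 12.1 the Safety Population holds implanted subjects and also those who "underwent the implant procedure but were never implanted, regardless of study completion status". No endpoint is excepted: "All safety analyses will be performed on the Safety population".

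**Follow-up without an implant.** Sections 5, 8.2 and 12.1 deal with subjects whose pulmonary artery branch is too small. Section 12.1 calls them ineligible but adds that "these subjects will be followed for 30 days for safety and all safety related data for these subjects will be provided". Section 8 states two-year follow-up for all subjects, while 8.3 gives visits only for implanted subjects.

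**Endpoint and time origin.** Section 9.1.2 defines sensor failure as an inability to obtain readings from the sensor after troubleshooting. Section 12 sets the clock: "The primary time point for safety analyses is 24 months post enrollment". Section 12.7.1 requires the lower one-sided 97.5% limit to exceed 90% for sensor failure and 80% for complications.

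**The concern.** There are two linked problems.

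The first is collection. Section 11.5 is the section that sites follow for reporting, and it contains the 3-day SAE deadline. Its window opens only once the implant has succeeded, yet catheterization and sensor delivery come before that moment. A site that applies the defined term strictly has no duty under 11.5 to report an event during those steps, or any event in a subject who never receives a sensor. The safety record of the implant step could then be incomplete, in a study whose safety analyses are meant to include failed attempts.

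The second is the sensor-failure denominator. A subject with no sensor cannot have a sensor failure. Because enrollment means implant, that subject also has no 24-month time point. Section 12.7.1 gives no rule for counting such subjects. Counted as failure-free, they could only raise the proportion tested against 90%.

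**Working it through.** **1. Passages side by side (collection)**

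| Place | What it implies |
|---|---|
| 11.5 with section 12 and Appendix F | Window opens at successful implant |
| 12.1 | Attempted-but-not-implanted subjects belong to the Safety Population |
| 11.1 Note 2 | Procedure events are adverse events |
| 11.3 | Insertion-procedure events count as device-related |
| Appendix A | AE assessment at the Baseline (Implant) visit |
| 5, 8.2, 12.1 | 30-day safety follow-up when the artery is unsuitable |
| Synopsis | Enrollment at consent plus eligibility |

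The first row conflicts with those below it to different degrees. The conflict with 12.1 and the 30-day follow-up is direct, since a never-implanted subject never enters the 11.5 window. The Appendix A mark is weaker evidence: for an implanted subject, surveillance could begin part-way through the Baseline visit. The synopsis differs only on the time before sensor release and on failed implants in suitable anatomy, because artery size is itself inclusion criterion 7.

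**2. Follow-up.** The 30-day rule is written only for an unsuitable artery. For a procedure abandoned for any other reason, section 8 (all subjects, two years) and 8.3 (implanted subjects only) do not settle what applies.

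**3. Sensor-failure denominator**

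*Inputs.* P0 = 0.90, P1 = 0.95, one-sided alpha 0.025, exact binomial test and n = 292 (12.3 and its table); 800 subjects (12.3). Section 12.7.1 does not name the interval method, so the exact test of 12.3 is assumed. The number m of never-implanted subjects is not given; the values below are assumptions.

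*Reproducing the plan.* With X ~ Bin(292, p) and success at X ≥ 273:
- P(X ≥ 273 | 0.90) = 0.0242
- P(X ≥ 273 | 0.95) = 0.9019

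Both match the table.

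*Adding m subjects counted as failure-free.* Let k be the number implanted and N = k + m. Let r be the smallest count with P(Bin(N, 0.90) ≥ r) ≤ 0.025. The m subjects supply m successes, so the implanted subjects need only r − m. The chance of passing is P(Bin(k, p) ≥ r − m), where p is the true freedom among implanted subjects.

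| k | m | N | r | r − m | Failures allowed, k − (r − m) | P(pass), p = 0.90 |
|---|---|---|---|---|---|---|
| 800 | 0 | 800 | 737 | 737 | 63 | 2.3% |
| 800 | 8 | 808 | 745 | 737 | 63 | 2.3% |
| 800 | 16 | 816 | 752 | 736 | 64 | 3.1% |
| 800 | 40 | 840 | 774 | 734 | 66 | 5.3% |
| 292 | 0 | 292 | 273 | 273 | 19 | 2.4% |
| 292 | 9 | 301 | 282 | 273 | 19 | 2.4% |
| 292 | 15 | 307 | 287 | 272 | 20 | 4.0% |

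With 292 implanted, m = 3 and m = 6 also leave the chance at 2.4%.

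*At the plan's alternative.* At p = 0.95 with 800 implanted, the chance of passing is at least 99.98% for every m shown. The reported proportion barely moves: for m = 40 it is (760 + 40)/840 = 95.2% against a true 95.0%.

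**4. Complications.** With n = 800 and P0 = 0.80, the exact test passes at 663 or more event-free (alpha 0.0218), which allows 800 − 663 = 137 events. At the 98.6% freedom that 12.3 quotes from CHAMPION, 800 × 0.014 = 11.2 events are expected.

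**The case against.** The strongest reply is that the intent is plain. Notes and definitions in section 11 bring procedure events in, the schedule places AE assessment on the day of implant, and unsuitable-artery subjects have a stated safety follow-up with their data to be provided. A reader might infer from 11.5 that the study would collect no peri-procedural events. The documents do not support that, and the point here does not claim it. What stands is that the operative reporting sentence uses a defined term whose definition excludes the events that the rest of the plan wants.

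On follow-up, the two-year statement in section 8 can be read as meaning enrolled, hence implanted, subjects. That removes the contradiction with 8.3, but it leaves procedures abandoned for other reasons with no stated follow-up.

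On the denominator, a reader might infer that the sensor-failure test has an inflated type I error. That would need several things the plan does not supply: a sizeable number of never-implanted subjects, a rule counting them as 24-month successes, and true freedom close to 90%. The section 12 time origin favours leaving them out, and if they are left out or censored the effect is close to nil. It is also unclear whether unsuitable-artery subjects, called ineligible, belong to the Safety Population at all; if not, the added group is smaller. These objections limit the size of the point. They do not remove the instruction in 12.1 to run every safety analysis on a population that includes subjects with no sensor.

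**Conclusion.** The point holds as two defects in the written rules. First, 11.5 read with section 12 and Appendix F contradicts 12.1 and the passages that provide for procedural and 30-day safety data. The consequence is a risk of incomplete or uneven reporting for the implant step; its size cannot be estimated from the documents. Second, the sensor-failure population is wrong as written and the counting rule is missing.

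The numerical effect of the second defect is conditional. With 800 implanted it ranges from nothing (8 added) to a rise from 2.3% to 5.3% (40 added), and only at true freedom of exactly 90% with added subjects counted as failure-free. No wrong result is predicted at the plan's own alternative. The complication verdict is not expected to change, since about 11 events are expected against 137 allowed; this rests on the CHAMPION figure carrying over. The text conflict is certain, whereas the inflation figures are illustrations on assumed counts.

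**What to change.** - **11.5:** start AE collection for every consented subject no later than the start of the catheterization/implant procedure, and include never-implanted subjects through their safety follow-up.
- **Enrollment:** use one definition in the synopsis, 11.5, section 12 and Appendix F.
- **Follow-up:** reconcile sections 5, 8, 8.2, 8.3 and 12.1 so that they cover every attempted-but-not-implanted subject, whatever the reason, and state whether unsuitable-artery subjects are in the Safety Population.
- **12.1 and 12.7.1, sensor failure:** analyse implanted subjects only. With 292 implanted at 95% freedom the power is the plan's own 90.2%, so no planned power is lost.
- **12.1 and 12.7.1, complications:** keep never-implanted subjects in the Kaplan-Meier analysis, censored at the end of their follow-up, and report their number and events separately. This needs a time origin that they possess, such as the procedure date. Do not count being event-free at 30 days as a 24-month success, which would repeat the denominator fault.

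The cost is minor amendment wording, one changed denominator and, if enrollment has begun, a check of baseline records for events before sensor release. Reported rates may be slightly less favourable.

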### 11.6. Adverse Event Reporting to Country Regulatory Authorities by the Sponsor

The Sponsor will report SAEs, SADEs and ADEs to the country regulatory authority, per local requirements.

### 11.7. Anticipated Adverse Events

Risks associated with the CardioMEMS™ PA Sensor or the implant procedure (in conjunction with RHC) or post-implantation complications, together with their likely incidence, are described in the User's Manual.

## Clinical Investigation Plan

### **12. STATISTICAL ANALYSIS**

The data will be summarized using univariate statistics (e.g., N, mean, standard deviation, median, minimum and maximum) or frequency (e.g., N, %) as appropriate for continuous or categorical variables, respectively.

The primary time point for safety analyses is 24 months post enrollment. Enrollment is defined as having a successful Sensor implant. The primary time point for effectiveness analyses is 12 months post enrollment.

Unless otherwise specified, all statistical tests will be 2-sided with a significance level of 0.05.

#### **12.1. Populations for Analysis**

**Safety Population:** The Safety Population consists of all subjects who received a Sensor implant or underwent the implant procedure but were never implanted, regardless of study completion status. All safety analyses will be performed on the Safety population.

Subjects who are found not to have an appropriately sized pulmonary artery branch and did not receive the Sensor implant will be considered ineligible for the study. However, these subjects will be followed for 30 days for safety and all safety related data for these subjects will be provided.

**Effectiveness Population:** The effectiveness population consists of all subjects who received a Sensor implant regardless of study completion status. All effectiveness analyses will be performed on the effectiveness population.

**Pooled Safety Population:** The Pooled Safety Population will consist of the Safety Population from this study and the Safety Population from other similar study(ies) (demonstrated to be poolable with this study) that have been combined to form a larger safety analysis population to permit more robust analyses.

**Pooled Effectiveness Population:** The Pooled Effectiveness Population will consist of the Effectiveness Population from this study and the Effectiveness Population from other similar study(ies) (demonstrated to be poolable with this study) that have been combined to form a larger effectiveness analysis population to permit more robust analyses.

#### **12.2. Sample Size Considerations**

##### **Effectiveness Sample Size Determination**

For the primary effectiveness endpoint of HF hospitalization rate during 1 year, 250 subjects will provide greater than 90% power to meet the efficacy goal, using a one-sample, one-sided Poisson rate test with alpha of 0.025.

The HF hospitalization (HFH) rate for Control and Treatment groups at 1 year in Part 1 of the CHAMPION trial were 0.75 and 0.52 (HFH/patient-year), respectively. For this trial, HF hospitalization rates at 1 year will be compared to the rate observed in the trial subjects 1 year prior to enrollment (i.e., 1.0 or greater). Using a one-sample, 1-sided Poisson rate test with alpha of 0.025 (equivalent to 2-sided test at alpha of 0.05) (see table below), at least 149 subjects will provide >90% power to show a difference between a Treatment rate as high as 0.75 (conservative estimate) and the subject's own

## Clinical Investigation Plan

historical rate from the year prior estimated at a minimum of 1.0. To account for early withdrawal, and to allow additional countries to enroll sufficient number of subjects each, 800 subjects will be enrolled.

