## Clinical Investigation Plan

Number of Subjects	Up to 800 subjects will be enrolled. Enrollment will be limited to 15% of the total study population at any one site.
Number of Sites:	This is a prospective, multi-center, open-label clinical trial to be conducted at up to 85 sites.
Safety Measures:	
Primary safety endpoints will be evaluated at 2 years: 1) freedom from device/system related complications and 2) freedom from pressure sensor failure.
 
Safety will also be assessed throughout the study by the frequency of Adverse Device Effects (ADEs), Serious Adverse Events (SAEs), and Serious Adverse Device Effects (SADEs).

Effectiveness Measures:	
The primary effectiveness endpoint is the annualized HF hospitalization rate at 1 year.
 
Supplemental analyses include mortality at 1 year, HF hospitalization or death at 1 year, patient compliance over the trial, training evaluation, and subgroup analyses.
 
Information regarding all hospitalization and deaths will be collected throughout the study.

Statistical Considerations:	
Primary Safety Endpoints            The primary safety hypotheses are that the device / system-related complication-free proportion of subjects will be at least 80% at 24 months (OPC used in the CHAMPION trial) and that the pressure sensor failure-free proportion of subjects will be at least 90% at 24 months (OPC used in the CHAMPION trial). Plotting and analysis of safety endpoints will also be displayed using Kaplan-Meier methods.            All safety analyses will be performed on the safety population.
 
Primary Effectiveness Endpoint            The primary effectiveness evaluation will compare the annualized HF hospitalization rate at 1 year compared to the HF hospitalization rate in the year prior to enrollment.            The effectiveness population consists of all subjects who received a sensor implant regardless of study completion status.
 
Supplemental Analyses            Mortality at 1 year will be analyzed. Plotting and analysis of mortality will be displayed using Kaplan-Meier methods.            The annualized HF hospitalization or death rate at 1 year in study will be compared to the HF hospitalization rate in the year prior to enrollment.

*This confidential document is the property of Abbott and shall not be reproduced, distributed, disclosed or used without the express written consent of Abbott*

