### 12.3. Safety Sample Size Determinations

The freedom from device-related complications observed in CHAMPION over 2 years was 98.6%. For the two-year primary safety endpoint of freedom from device-related complications, using an exact one-sided test for one-sample binomial proportions with alpha of 0.025 (equivalent to 2-sided test at alpha of 0.05) (see table below), a sample size of 137 subjects will provide greater than 90% power to detect a difference as small as 10% from the null proportion rate of 0.80 (i.e., objective performance criterion of 80%). For sensor failures at 2 years, a sample size of 292 subjects provides greater than 90% power to detect a difference as small as 5.0% from the null proportion rate of 0.90 (i.e., objective performance criterion of 90%)(see table below).

To account for early withdrawal, and to allow additional countries to enroll sufficient number of subjects each, 800 subjects will be enrolled.

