### 12.8.2.5. Subgroup Analyses

The effectiveness analyses will be evaluated in each of the following subgroups:

- 1) Women
- 2) Men
- 3) Reduced Ejection Fraction (< 40%)
- 4) Preserved Ejection Fraction ( $\geq 40\%$ )
- 5) Ischemic Etiology
- 6) Non-ischemic Etiology
- 7) With ICD/CRT-D
- 8) Without ICD/CRT-D

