## Clinical Investigation Plan

			
Informed consent process
 
Ethics approval
 
Adverse event definition revised
 
For unexpected serious adverse device effect, the term UADE is used for studies following FDA regulations and USADE for studies following ISO 14155 regulations
 
Reporting SAE, ADE, SADE timelines revised
 
Revise the anticipated adverse events list to ensure consistency between study documentation (CIP, Informed Consent Template and the device User's Manual)
	
No annual approval renewal needed for countries OUS
 
Adverse event definition clarified
 
UADEs replaced by USADEs
 
Reporting SAE, ADE, SADE timelines revised
 
Added Allergic reaction, bruising, chest pain, nausea and sepsis to the CIP; added hemoptysis and sepsis to the PIS

2	C	18Apr2018	
Study Population
 
Number of subjects/sites
 
International Normalized Ratio (INR)
	
Removed requirement for 35% women; this was only required by FDA for US PAS
 
Increased to 800 subjects/85 sites in order to expand to other countries in EU, AUS
 
The INR has been revised to reflect institution standards.

*This confidential document is the property of Abbott and shall not be reproduced, distributed, disclosed or used without the express written consent of Abbott*

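### The primary Poisson limit ignores variation between sites; a site-clustered limit and a descriptive country summary would be a cheap improvement

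*Combined protocol and SAP*

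**What the plan says.** - **Primary analysis (12.8.1).** One pooled on-study rate at 12 months is compared with the prior-year rate by a one-sample, one-sided Poisson test. The endpoint is met if the upper 97.5% limit lies below the prior-year rate. There is no site or country term.
- **Sample size (12.2, and again in 12.3).** Early withdrawal is given as one reason. The sentence goes on: "to allow additional countries to enroll sufficient number of subjects each, 800 subjects will be enrolled". The synopsis words the figure as a ceiling: "Up to 800 subjects will be enrolled". The revision history (Appendix G) explains the change as "Increased to 800 subjects/85 sites in order to expand to other countries in EU, AUS".
- **Concentration (synopsis).** "Enrollment will be limited to 15% of the total study population at any one site". This is the only rule that refers to site size, and it limits enrollment without affecting the analysis.
- **Subgroups (12.8.2.5).** "The effectiveness analyses will be evaluated in each of the following subgroups": sex, ejection fraction, etiology, and ICD/CRT-D status. Country, region and site are absent.
- **Pooling (12.1).** Poolability is mentioned only for combining this study with other studies.

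**The concern.** Two features of the study make different rates at different sites plausible. First, the device does nothing by itself: under Section 5 and Appendix C, site clinicians review pressures, may reset thresholds for each patient, and change medication using their own judgment. Second, Appendix F defines a heart failure hospitalization by a stay of at least 24 hours, so local admission practice feeds directly into the count.

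A pure Poisson limit has no room for such variation. If the result is meant to describe use of the device beyond the particular sites enrolled, the limit is too narrow, and the one-sided error rate exceeds the stated 0.025. Separately, expansion to more countries is one of the reasons given for the sample size, yet a reader of the final report would have no planned way to see whether the pooled result is broadly similar across countries.

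**Working it through.** **1. The plan's own figure.** With n = 149 and a null rate of 1.0, the largest count that rejects at one-sided 0.025 is 125. Actual alpha is 0.0247 and power at 0.75 is 0.9016, as in the table in 12.2. With 800 subject-years the rule passes at 744 events or fewer (observed rate 744/800 = 0.930; actual alpha 0.0239).

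**2. Variance inflation.** Let site i contribute m_i subject-years, with true rate λ times a site factor of mean 1 and coefficient of variation CV. The variance of the total count, divided by its Poisson variance, is

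VIF = 1 + CV² × λ × (Σm_i² / Σm_i).

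Inputs from the documents: 800 subjects, 85 sites, cap of 15% (120). Assumptions: CV of 10% to 20% (the documents give none), one full year per subject, and mean rate 0.6, which lies between the rates of 0.52 and 0.75 in 12.2.

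- Equal sites: Σm²/Σm = 800/85 = 9.41.
- One site at the cap, the other 84 equal at 680/84 = 8.10: (14,400 + 84 × 8.095²)/800 = (14,400 + 5,505)/800 = 24.88.

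| CV | Layout | VIF at λ = 0.6 | VIF at λ = 1.0 |
|---|---|---|---|
| 10% | equal | 1.06 | 1.09 |
| 10% | one site at 120 | 1.15 | 1.25 |
| 20% | equal | 1.23 | 1.38 |
| 20% | one site at 120 | 1.60 | 2.00 |

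The cap would permit more than one site at 120, which would give larger values.

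**3. Effect on the limit at an observed rate of 0.75.**
- Poisson: 0.75 + 1.96 × √(0.75/800) = 0.810.
- VIF 1.60: 0.75 + 1.96 × √(0.75 × 1.60/800) = 0.826.
- VIF recalculated at λ = 0.75, that is 1 + 0.04 × 0.75 × 24.88 = 1.75: 0.829.

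All are far below 1.0.

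**4. Where the decision could change.** On the log scale the rule passes if r × exp(1.96 × √(VIF/(800r))) < 1.
- VIF = 1, r = 0.930: 0.930 × exp(1.96/√744) = 0.999, which agrees with the exact threshold.
- Largest scenario, r = 0.904: VIF = 1 + 0.04 × 0.904 × 24.88 = 1.90, and 0.904 × exp(1.96 × √(1.90/723.2)) = 0.9995.

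So in these scenarios the two limits can disagree only for observed rates between about 0.90 and 0.93.

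**5. Error rate when the true mean rate is 1.0.** Approximately Φ(−1.96/√VIF), with the last column of the table: 0.030 to 0.040 at CV 10%, and 0.047 to 0.083 at CV 20%. Simulation gave about 0.028 to 0.037 and 0.047 to 0.079, against a nominal 0.025.

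**6. The country reason.** The largest sample that a stated calculation uses is 292 (sensor failure, 12.3); the effectiveness section states 250. No withdrawal rate is given. Withdrawal alone would have to be 1 − 292/800 = 63.5%, or 1 − 250/800 = 69%, to account for 800. Country expansion is therefore a real part of the justification, though not the only part.

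**The case against.** **The Poisson limit is not wrong for every purpose.** If the enrolled sites are taken as fixed, the total count is still Poisson around the average rate at those sites, and the planned limit is correct for that average. This stands. The clustered limit is needed when the sites stand for wider use, which is the natural reading of an objective set in real-world or commercial use.

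**The CV is assumed and the effect is modest.** This also stands. Nothing in the documents supports 10%, 20% or any other value, and at the rates the plan expects the conclusion would not change.

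**No country objective is stated.** Correct. The study objective is overall safety and effectiveness, 800 is a ceiling in the synopsis, and expansion may have been operational. Nothing obliges the sponsor to draw conclusions by country.

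**Stronger readings that the documents do not support.**
- A reader might infer that a pooled pass is an error if half the subjects are in countries with no change (1.0) and half in countries at 0.80. The pooled rate is then 0.90 and the rule passes 82% of the time. But the hypothesis in 12.8.1 concerns the overall rate, and 0.90 is below 1.0, so 82% is correct power for the average.
- A reader might infer that each country needs 149 subjects. That figure gives 90% power for a test at 0.75 against 1.0. A descriptive estimate has no such minimum.
- A reader might treat the undefined sufficient number per country as a fault in its own right. It is a missing detail, and defining it would change no analysis.

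**Conclusion.** The point holds as an improvement to the primary limit. No stated figure is wrong, and the pooled test is a valid test of the average under its own assumptions. Those assumptions exclude any between-site variation, in a study where such variation is plausible and one site may hold 120 of 800 subjects. The inflation is 1.06 to 1.15 times the Poisson variance at an assumed site CV of 10%, and 1.23 to 1.60 times at 20%, for a mean rate of 0.6 with either equal sites or one site at the cap. It is unlikely to reverse a clear result and matters mainly for an observed rate close to 0.93.

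The country part is smaller: a descriptive summary that fits one of the stated reasons for the sample size. A reader might expect it to reveal countries without device benefit. It cannot. Entry requires a heart failure hospitalization in the prior 12 months, so the prior-year rate is at least 1.0, while CHAMPION controls ran at 0.75. A country with no device benefit could still show a fall. That limitation belongs to the own-history comparator, and a country table does not remove it.

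**What to change.** 1. **Section 12.8.1.** Compute the one-sided 97.5% upper limit for the on-study rate from an intercept-only Poisson model with log follow-up time as offset and a robust variance clustered on site. Keep the comparison with the prior-year rate as planned; no period term is needed. Specify a small-sample correction. A site holding 15% of subjects pulls the fitted mean toward itself, so its squared residual shrinks by about (1 − 0.15)² = 0.72. The correction reduces the resulting understatement of variance but may not remove it entirely. The pure Poisson limit can be kept as a sensitivity analysis.
2. **Section 12.8.2.5.** Add country, or region with small countries grouped by a rule fixed in advance, as a descriptive consistency summary: prior-year and on-study rates with 95% confidence intervals. State that it does not test benefit within any country.

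The cost is a slightly wider primary limit, a short change of wording and one table. Subjects are already identified by site, and so by country, so no new data are needed.
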